13.3.5 Rules for concomitant therapy in participants receiving Leflunomide

All treatments being taken by the participants on entry to the trial or at any time during the trial in addition to the investigational medicinal product are regarded as concomitant treatments and must be documented in the participant's hospital notes; only concomitant treatments relevant to this trial will be recorded on the eCRF as required.

Concomitant medications felt to be clinically indicated would be allowed during the study so long as they do not interfere with the investigational medicinal products (please refer to the applicable SmPC/IB).

Clinicians should review the current DMARD being prescribed and use clinical judgement when initiating any new therapies known to interact with LEF.

Warfarin can interact with leflunomide. Warfarin dose may need to be adjusted alongside LEF therapy. GPs are informed of this as part of GP letter.

13.3.6 Leflunomide Dosing and Frequency

The STERLING trial specifies a Starting Dose, Target Dose and Minimal Dose for LEF. A dose titration procedure will be used to establish a Maximum Tolerated Dose of LEF for each participant, which will be between 10mg twice per week and 20mg daily.

An initial three-day loading dose of LEF is suggested in the SmPC but this is rarely utilised in clinical practice in rheumatology and will not be used in this trial.

The participant's GP should be informed in writing of all dose escalations, reductions and other modifications and should be requested to update this dose information on the participant's healthcare record.

The Starting Dose, Target Dose and Minimal Dose are specified in Table 2.

Leflunomide Dosing	Dose, reason
Starting Dose	10mg daily for most participants 10mg alternate days for individuals with relevant co-morbidities e.g., frailty, at the physician's discretion
Target Dose (if tolerated)	20mg daily is the maximum permitted dose.
Minimal Dose	10mg twice per week If this is not tolerated, stop LEF.
Maximum Tolerated Dose	Established for each individual by dose titration; should not exceed 20mg daily.

Table 2

13.3.7 Leflunomide Starting Dose

The Starting Dose of LEF will generally be 10mg daily but may be reduced to 10mg alternate days for individuals with relevant co-morbidities, for example significant frailty, at the physician's discretion.

Participants will remain on this dose until at least the week 4 follow-up telephone consultation with the site team.

13.3.8 Leflunomide Target Dose

The earliest timepoint for potential dose escalation will be following the week 4 telephone assessment but may occur following any of the telephone assessments up to the week 26 clinical assessment.

Dose escalation should only be performed once the latest DMARD monitoring blood tests and blood pressure (see section 13.3.4) have been checked to assess for any biochemical/haematological abnormalities and blood pressure has been taken to exclude hypertension (value should be below 140/90).

13.3.9 Leflunomide Minimal Dose

The Minimal Dose of LEF will be 10mg twice per week. If this is not tolerated, LEF will be stopped, and participants will continue therapy with Usual Care (steroids) alone; no further DMARD will be offered (50).

13.3.10 Duration of Treatment

Participants in the DMARD arm will commence LEF only after stopping MTX. Providing it is tolerated and there is no toxicity, the LEF treatment will continue until the final study visit at 18 months.

13.3.11 Leflunomide compliance

Where possible within the conduct of this trial, local systems and processes to reduce the risk of LEF dosing errors should be followed.

Participants will be advised to maintain a record of their DMARD doses in addition to their steroid doses and provided with a diary for this if required. Details of DMARD compliance will be collected by the site research team during telephone and face-to-face assessments.

13.3.12 Leflunomide Delays and Dose Modifications

Please also see section 13.4.1 regarding Laboratory Abnormalities and Infections.

13.3.13 Most frequently anticipated toxicities of LEF

The commonest side-effect of LEF is gastrointestinal upset including abdominal pain, loose stool or diarrhoea, and less commonly nausea, vomiting, or raised liver function tests. These adverse effects are most prominent in the first two weeks of therapy and tend to improve thereafter (50). A rise in blood pressure is uncommon and can usually be managed with antihypertensive therapy. Hair thinning may occur. Cytopenia is described but is not common. LEF-associated pneumonitis is very rare. LEF toxicities may persist after stopping therapy due to the long half-life of LEF in the body. If necessary, a cholestyramine washout procedure reduces the LEF levels to very low levels (50).

13.3.14 Leflunomide and pregnancy

LEF is a teratogen and must not be taken in pregnancy. In line with the SmPC, both male and female participants must use contraception (see appendix 2) for the duration of their treatment with leflunomide. In participants who are women of child-bearing potential (WCBP) LEF must be stopped two years in advance of trying to conceive. If a waiting period of up to approximately 2 years under reliable contraception is considered unpractical washout with cholestyramine or activated powdered charcoal according to the processes described within the SmPC must be initiated. In the event of unplanned pregnancy LEF should be stopped immediately.

participants wishing to conceive should undergo LEF washout with cholestyramine according to the processes described within the SmPC. For participants who are women of child-bearing potential who do not wish to undergo washout with cholestyramine then contraceptive measures (see appendix 2) must be used for 2 years after the end of trial treatment. In the event of unplanned pregnancy LEF should be stopped immediately (51).

13.4 PROCESSES AND CONSIDERATIONS COMMON TO BOTH DMARDS

13.4.1 Laboratory Abnormalities and Infections

A temporary DMARD treatment interruption may be required (managed at the investigator's discretion) under circumstances such as those described below.

Abnormal LFTs

- ALT or AST elevation of ≥ 3 times ULN, dose interruption is recommended.
- ALT or AST elevation $\geq 5x$ ULN, discontinuation of DMARD treatment is recommended.
- If ALT or AST elevation of ≥ 3 times ULN and
 - Total bilirubin $> 2x$ ULN or INR > 1.5 ULN, and
 - Alkaline phosphatase $> 2x$ ULN and
 - Presence of worsening fatigue, nausea, vomiting, fever, rash, or eosinophilia,discontinuation of treatment is recommended.

Infections

Clinical signs which suggest the possibility of drug toxicity may include severe or frequent minor infections, mucositis and pneumonitis and should be interpreted by the investigator and lead to dose interruption if indicated. Multiple dosing interruptions up to 8 weeks at any one time are allowed if necessary.

Neutropenia

Absolute neutrophil count decrease should be managed according to clinical judgment; a decrease to $< 1 \times 10^9/L$ ($1 \times 10^3 /\mu L$) should however result in treatment interruption. Study treatment should commence after increase of the neutrophil count to $\geq 1 \times 10^9/L$ and in line with clinical judgment. Treatment is continued as long as no further safety concerns arise. Multiple dosing interruptions up to 6 weeks at any one time are allowed if necessary.

The participant's welfare is the responsibility of the investigator. Therefore, the investigator must decide, based on risk-benefit assessment, what is needed to ensure the safety of the treatment. These options include deciding when unscheduled or repeat laboratory testing is indicated, and if a temporary interruption or discontinuation of treatment +/- concomitant medication is appropriate.

13.3.2 Cessation of DMARD

Participants are permitted to stop DMARD within the trial once six months have elapsed since they stopped taking steroids.

13.3.3 Procedures if participant transfers to another hospital

The DMARD prescriptions are issued by the hospital Study Site. Therefore, if the participant moves interstate (between South Australia, Western Australia or Victoria), then the local investigator should verify that DMARD prescription and blood monitoring arranged by the Site Research Team can safely continue and transferred providing participants are willing to continue engagement with the follow-up procedures. If the Participant moves to another state, they would have to withdrawn from the study with safety of ongoing / removal of treatment communicated with the participants GP.

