13.4 WITHDRAWAL OF TREATMENT

In line with usual clinical care, cessation or alteration of regimens at any time will be at the discretion of attending clinicians or the participants themselves. All participants withdrawn from treatment or prescribed alternative treatment will still attend for follow-up assessments unless unwilling to do so and eCRFs will continue to be completed.

The PI, or delegate should make every effort to ensure that the specific wishes of any participant who wishes to withdraw consent for further involvement in the trial are defined and documented using the Withdrawal CRF in order that the correct processes are followed by the CTRU and site following the withdrawal of consent. It should be made clear to any participant specifically withdrawing consent for further data collection in a CTIMP that data pertaining to safety will continue to be collected for regulatory reporting purposes and will be included in any safety analysis. In addition, it is suggested that the participant is made aware of the fact that if any significant new information becomes available in regard to the treatment they have received in the trial, it may be necessary to contact them in the future.

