Questionnaires completed at baseline (week 0) will be administered by the research staff via a paper booklet before the participant has been informed of the randomisation allocation. Participants will be given the choice of completing questionnaires at all subsequent time points either on paper or electronically. For participants wishing to complete the questionnaires electronically they will be given the option of receiving an email or text message with a link to their questionnaire. Participants' preferred method of questionnaire administration and completion will be collected during the trial randomisation process and applicable contact details, postal address/email address/mobile phone number, collected. The CTRU will send questionnaires to participants directly. Non-respondents will receive reminders by their pre-stated preferred method of communication. The CTRU will contact sites at intervals throughout the study to ensure that consenting participant's contact details and status have not changed and that it is still appropriate to send them a questionnaire.

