16 OUTCOME MEASURES

16.1 PRIMARY OUTCOME MEASURE

The primary outcome measure is mean participant reported cumulative prednisolone dose between randomisation and 18 months post-randomisation, reported by participants via a monthly questionnaire.

Where a participant receives an alternative steroid medication to prednisolone, the steroid dose will be converted to a “Prednisolone equivalent dose” prior to analysis.

Intercurrent events of interest are:

- Death – to be handled under a treatment policy strategy;
- Discontinuation of trial treatment (including crossover to other arm) – to be handled under a treatment policy strategy;

Although steroid diaries are a part of routine clinical care, we acknowledge a lack of data as to the accuracy of participant-completed steroid diaries as a means to track medication usage. We have identified only small-scale results, incompletely reported and for different populations, claiming that medication diaries have satisfactory test-retest reliability (62) and that comparable methods of medication use surveillance lead to similar reported adherence levels (63).

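### The relocation rule in 13.3.3 ends study participation, not just site-delivered treatment, and so stops steroid-dose follow-up that could still be collected

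*Protocol*

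**What the plan says.** Section 13.3.3 (Procedures if participant transfers to another hospital) opens with its reason: "The DMARD prescriptions are issued by the hospital Study Site". A participant who moves between South Australia, Western Australia and Victoria can be transferred and can continue, once the investigator has checked that prescribing and blood monitoring can safely go on. For a move anywhere else: "If the Participant moves to another state, they would have to withdrawn from the study". The GP is then told about the treatment position. No withdrawal of consent is involved, and no data collection after the move is mentioned.

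Other sections treat stopping treatment and stopping follow-up as separate matters:

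- Section 13.4 (Withdrawal of treatment): "All participants withdrawn from treatment or prescribed alternative treatment will still attend for follow-up assessments unless unwilling to do so".
- Section 14.12: when the clinician takes a participant off treatment, scheduled data collection goes on unless the participant expressly withdraws consent to it.
- Section 14.15: follow-up runs until death or the end of the follow-up period. Relocation is not an exception.
- Section 16.1: the primary outcome is cumulative prednisolone dose over 18 months, "reported by participants via a monthly questionnaire". On intercurrent events it says: "Discontinuation of trial treatment (including crossover to other arm) – to be handled under a treatment policy strategy".
- Section 14.10: "The CTRU will send questionnaires to participants directly", on paper or through an email or text link.
- Section 18.1: the intention-to-treat population is everyone randomised.

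**The concern.** A move can end what a site is able to deliver, namely prescribing, monitoring and clinic visits. It does not by itself end what the CTRU can collect. Section 13.3.3 joins the two, so a site that follows it literally will close follow-up for a participant who has not asked to leave and could still answer the monthly steroid questionnaire.

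Under a treatment-policy strategy, the steroid dose taken after trial treatment stops is part of the outcome being estimated. If a move ends DMARD supply, that is a discontinuation of trial treatment, and the doses after it are the ones the strategy needs. The rule therefore creates missing primary-outcome data that the protocol's own arrangements could avoid. An analysis plan can model those data but cannot recover them.

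**Working it through.** **1. The passages side by side**

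| Situation | Treatment | Follow-up data |
|---|---|---|
| Withdrawn from treatment (13.4, Withdrawal of treatment) | stops or changes | continues unless unwilling |
| Clinician takes participant off treatment (14.12) | stops | continues unless consent withdrawn |
| Any participant (14.15) | not addressed | to death or end of follow-up |
| Move among the three site states (13.3.3) | may continue after transfer | continues |
| Move to any other state (13.3.3) | continuation or removal communicated to GP | ends with study withdrawal |

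Only the last row ends follow-up without the participant's choice. Its stated reason bears on the treatment column alone.

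**2. What stops being collected.** Section 14.10 sends the steroid questionnaire every 4 weeks from week 4 to week 80, which is 80 / 4 = 20 questionnaires. The larger packs after baseline are at weeks 12, 24, 36, 48, 60, 72 and 80, which is 7. As an illustration, a participant who moves just after week 24 has been sent 24 / 4 = 6 steroid questionnaires and 2 packs. The remaining 14 and 5 would not be sent. All of them go out from the CTRU, not from the site.

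**3. The planned sample size, reproduced.** Inputs from section 17: 30% reduction, CV 0.78, two-sided 5%, 90% power, 20% attrition, N = 200.

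- SD on the log scale: √ln(1 + 0.78²) = 0.689. Difference: |ln 0.70| = 0.357.
- Normal approximation: n per arm = 2 × 0.689² × (1.960 + 1.282)² / 0.357², rounded up to 79. Total 158 / 0.8 = 198.
- Noncentral t: 80 per arm, 160 / 0.8 = 200, power 90.2%. This matches the plan.
- At CV 0.94 (SD 0.796) with 160 analysed, power is 80.4% (t) or 80.9% (normal). The statement of at least 80% also holds.

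**4. Size of the loss.** The documents give no relocation rate, so the fractions below are assumptions. The table takes the least favourable case: every mover is additional to the 20% attrition and contributes nothing to the analysis (normal approximation).

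| Movers among the 50 (assumed) | Analysed | Power, CV 0.78 | Power, CV 0.94 |
|---|---|---|---|
| 0% (0) | 160 | 90.5% | 80.9% |
| 2% (1) | 159 | 90.4% | 80.7% |
| 5% (2.5) | 157.5 | 90.1% | 80.3% |
| 10% (5) | 155 | 89.6% | 79.7% |

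With the t-test, losing 5 takes power at CV 0.78 from 90.2% to 89.3%. If the movers fall within the 20% allowance (40 of 200), the analysed number stays at 160 and power stays as planned.

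**The case against.** Much of the case on the other side stands.

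- **Estimand.** A reader might infer that the rule directly contradicts the treatment-policy estimand. It does not. Section 16.1 lists death and discontinuation of trial treatment as intercurrent events. Relocation and study withdrawal are not listed, and loss to follow-up is a missing-data matter under 18.5. The link is indirect, through the discontinuation that a move may cause. The direct conflict is with 13.4 (Withdrawal of treatment), 14.12 and 14.15.
- **Data thrown away.** This too might be inferred. Section 14.12 keeps and analyses what was collected before withdrawal of consent, and nothing suggests that a mover's earlier data would be dropped. The loss is of later data only.
- **Power.** Section 17 allows 20% attrition without limiting its cause, so movers may already be counted. The table above is an upper bound for the rates assumed.
- **Informative loss.** One could suppose that people in this age group move because their health is failing. The documents say nothing on this, so the point does not rest on it.
- **Usual care.** The sentence refers to any participant, yet it sits among DMARD provisions and may be meant for that arm only. If it covers both arms, usual care is not free of the site either: 7.2 and 12.6 make the steroid taper a site responsibility.
- **Telephone contacts.** These are made by the site team and cover safety and dosing (14.6), so they may not survive a move. Their number is also inconsistent: seven weeks in 7.4.1, four in 14.2. The argument needs only the CTRU questionnaires. Section 14.10 does have the CTRU check with sites that sending them is still appropriate, but that check can be made for someone who has moved.

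None of this explains why a centrally sent questionnaire must end when a site can no longer prescribe. Imputation is a remedy for unavoidable loss, not grounds for a rule that creates it.

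**Conclusion.** The concern holds as a wording conflict with a small, avoidable cost. Read literally, 13.3.3 withdraws people from the study for a reason that concerns site prescribing. It is out of line with the three sections that keep participants in follow-up unless they are unwilling or withdraw consent. The consequence is missing later steroid-dose and questionnaire data in an intention-to-treat analysis.

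The size depends on a relocation rate that the documents do not give. At an assumed 2–10% of the 50 Australian participants, 1 to 5 people would have incomplete primary-outcome data. At most about 1 percentage point of power would be lost, and none if those losses fall within the 20% allowance. Neither the sample size nor the validity of the primary analysis is in doubt. The rule deserves correction because it is cheap to correct and because data that were never requested cannot be recovered later.

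**What to change.** Reconcile 13.3.3 (Procedures if participant transfers to another hospital) with 13.4 (Withdrawal of treatment), 14.12, 14.15 and 16.1. State that:

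- a move out of the site states does not in itself end study participation;
- the CTRU's 4-weekly and 12-weekly questionnaires continue to week 80 unless the participant withdraws consent to them;
- remote contacts continue where the site can still make them.

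The wording should also say whether the provision covers both arms. How treatment is managed after a move is a separate matter, and nothing is proposed on it here.

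The cost is a sentence or two in the protocol. The postal, email and text routes already exist, and the CTRU already checks for changed contact details. Sample size and analysis are unchanged. Items that need a clinic visit, such as the PMR-AS, would still be missing for these participants.

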13.3.4 Further therapy post-trial

DMARD may be continued beyond the end of the study if clinically indicated and if local procedures allow.

13.4 WITHDRAWAL OF TREATMENT

In line with usual clinical care, cessation or alteration of regimens at any time will be at the discretion of attending clinicians or the participants themselves. All participants withdrawn from treatment or prescribed alternative treatment will still attend for follow-up assessments unless unwilling to do so and eCRFs will continue to be completed.

The PI, or delegate should make every effort to ensure that the specific wishes of any participant who wishes to withdraw consent for further involvement in the trial are defined and documented using the Withdrawal CRF in order that the correct processes are followed by the CTRU and site following the withdrawal of consent. It should be made clear to any participant specifically withdrawing consent for further data collection in a CTIMP that data pertaining to safety will continue to be collected for regulatory reporting purposes and will be included in any safety analysis. In addition, it is suggested that the participant is made aware of the fact that if any significant new information becomes available in regard to the treatment they have received in the trial, it may be necessary to contact them in the future.

14 ASSESSMENTS/SAMPLES/DATA COLLECTION

14.1 SUBMISSION OF TRIAL DATA

Informed Consent Documents, Serious Adverse Events (SAE), Suspected Unexpected Serious Adverse Reaction (SUSAR) and Participant Questionnaire Booklets will be collected via paper case report forms. CTRU will provide an electronic copy of these forms to be printed and completed by research staff at site and the information sent to CTRU, usually by electronic secure file transfer. All other data collection will be via Remote Data Entry (RDE) on electronic case report forms (eCRFs) managed by the CTRU at the University of Leeds. Access to the live STERLING database will be provided by the CTRU following sites being authorised to open to recruitment; guidance on RDE and completing eCRFs will be provided.

Data must only be completed by personnel authorised to do so by the Principal Investigator, as recorded on the trial-specific Authorised Personnel Log.

Where additional documentation is required by CTRU, for example hospital reports and letters, it is the responsibility of staff at research sites to redact all personal identifiable data prior to sending to CTRU. Such records should only include trial number, initials and date of birth to identify the participant. The exception to this is the participant consent form, where the participant's name and signature must not be redacted.

Participating hospitals will be expected to maintain a file of essential trial documentation (Investigator Site File) that will be provided by CTRU, and where applicable, keep copies of all sites completed paper CRFs for the trial (with the exception of QoL & Healthcare Resource use questionnaires).

14.2 SCHEDULE OF EVENTS.

Not included in this table: on reaching below 5mg prednisolone or equivalent for the first time, a 9am cortisol blood test should be performed (sections 14.6 & 14.8).

Participant Consent	Follow-up schedule (weeks);							Telephone Contact (Weeks)	DMARD monitoring blood tests	Blood Pressure (LEF only)
	Screening	Baseline (0)	12	24	36	48	80	4, 8, , 60, 72	As per local guidelines ††	As per local guidelines ††
Target Visit Window	Max. 6 weeks between Screening and Baseline		-/+ 2 weeks	-/+ 2 weeks	-/+ 2 weeks	-/+ 2 weeks	-/+ 2 weeks			
Written Informed Consent/Witnessed verbal informed consent	x									
Reg and Rand										
Registration	x									
Randomisation		x								
Trial Assessments			12	24	36	48	80			
Eligibility Checks	x	x								
Steroid Use Review		x	x	x	x	x	x	x		
DMARD Use Review if applicable			x	x	x	x	x	x		
Medical History		x	x	x	x	x	x			
AEs/SAEs review			x	x	x	x	x	x		
Chest X-Ray*	x									
Pregnancy Test	x									
RF [§]	x									
ACPA [§]	x									
U&E	x	x	x	x	x	x	x		x	
FBC	x	x	x	x	x	x	x		x	
Liver Function Test	x	x	x	x	x	x	x		x	
HbA1C		x	x	x	x	x	x			
CRP (Also needed for PMR-AS)	x	x	x	x	x	x	x			
ESR		x	x	x	x	x	x			
Physical Examination	x	x	x	x	x	x	x			
Vital Signs	x	x	x	x	x	x	x			
PMR Activity Score		x	x	x	x	x	x			
(PMR-AS) Number of minutes of morning stiffness		x		x				x		
(PMR-AS) Upper limb elevation / active shoulder abduction		x		x				x		
(PMR-AS) VAS global assessment (physician)		x		x				x		

Steroid Free Remission								x		
------------------------	--	--	--	--	--	--	--	---	--	--

* a report from a chest x-ray performed within the 6 months prior to the screening visit is acceptable to confirm eligibility providing that no evidence of interstitial lung disease or tuberculosis or active.

† As a guide the British Society for Rheumatology DMARD monitoring guidelines recommend FBC, U+E and LFT: every two weeks until on stable dose for six weeks, then monthly for three months and quarterly thereafter. Blood pressure should be measured at the same timepoints as these blood tests.

‡ Providing the results of the prior test are acceptable (see section 13.4.1), a window will be allowed one week either side of the scheduled date during the first six weeks, two weeks either side of the next scheduled date for the next three months and one month either side of the next scheduled date thereafter

§ Rheumatoid factor (RF) and anti-citrullinated peptide antibody (ACPA/anti-CCP) both within local laboratory reference range at or within the 12 months prior to the screening visit

